5.2. Efficacy study endpoints

Primary endpoint

Incidence of Ng plus Ct detected at any site.

Numerators: Cumulative number of laboratory-confirmed diagnoses of Ng plus Ct in 12 months in screening/non-screening arms. Each participant can only contribute one diagnosis of Ct and one diagnosis of Ng per (scheduled or unscheduled) visit - regardless of number of sites infected. Thus each participant can contribute up to 2 diagnoses (Ct/Ng) at each (scheduled or unscheduled) visit. The numerator includes laboratory-confirmed diagnoses made between scheduled visits, performed inside or outside of the study.

Denominators: Number of scheduled study visits with available results for the diagnosis of Ng/Ct. The denominator does not include unscheduled visits.

The diagnosis of Ng and Ct will be made via nucleic acid amplification testing (NAAT) performed on rectal and pharyngeal swabs and urine.

If the person urgently requires knowing if they are infected with Ng/Ct or not this will be done by repeat testing for these infections. If this test is positive for Ng/Ct then this will be counted as an intervisit infection in the final analysis.

In the primary analysis, the primary endpoint (as described above) includes all Ng/Ct diagnoses. Hence it is implicitly assumed that every diagnosis is a new infection. It is however possible that an Ng/Ct infection detected at the 3 to 12 month visit in the non-screening arm is simply a non-resolved infection from the prior visit. This could spuriously increase the measured incidence in the non-screening group. Because this risk only applies to the non-screening arm it results in a bias towards exaggerating the effect of screening on incidence. As such if our study finds that non-screening is non-inferior to screening this finding could not be explained by this bias. In a sensitivity analysis, the numerator of the primary endpoint will only include diagnoses if there was a negative test result at the prior visit.

Because any positive Ng/Ct test from the test of cure visits is considered a non-resolved old infection, these will not be included in the primary or secondary outcomes as new infections. If however the test of cure was to assess if an Ng infection had cleared and a new Ct infection was detected at the test of cure visit then this would be included as a new infection in the primary and secondary study outcomes.

Secondary endpoints

- 1) Antimicrobial exposure will be measured as number of standard doses per 1000 person-years based on standard WHO and ECDC methodology [1]. Data on all antimicrobials consumed will be collected at each study visit and will include antimicrobials consumed at other health facilities such as at participant's General Practitioner. Only start- and stop date of antimicrobial consumption is collected. It is assumed that standard treatment is received. See table below for standard treatment of STIs. If there is no information on type of Chlamydia infection, assume non-LGV. For other infections, collect information about standard treatment from investigators. The dose can then be converted to DDD standard doses based on WHO methodology [1].

Infection	Antibiotic	Dose	Duration	DDD (standard dose)
Chlamydia (LGV)	Doxycycline	100 mg 2x/day	21 days	2/day
Chlamydia (non LGV)	Doxycycline	100 mg 2x/day	7 days	2/day
Chlamydia (non LGV)	Azithromycin	1g oral	One dose	3.3

Gonorrhea	ceftriaxone + azithromycin	1g IMI +2g oral	Each one dose	0.5 ceftriaxone + 6.6 azithromycin
Syphilis	benzathine penicillin	2.4 mu (2.4mu= 1836 mg)	Either 1 or 3 doses	0.51/dose
Hepatitis C	None			

- 2) Incidence rate of symptomatic Ng and Ct. Similar to the primary endpoint but only taking into symptomatic infections. This information will be collected at all visits and will include episodes of symptomatic Ng and Ct diagnosed elsewhere as long as these were laboratory confirmed diagnoses – either based on molecular testing or in the case of Ng, culture.
- 3) Incidence rate of syphilis. The European IUSTI case definition of a syphilis infection will be followed [2].
- 4) Incidence of HIV
- 5) Economic impact of cessation of 3x3 screening in MSM in Belgium
- 6) Participants' perception/experience and preference for screening vs. no screening (only for ITM subjects)

6. Interim analyses

Interim analyses are planned at two time points: once 50% and 100% of all study recruits have passed their 6 month visit. For the first interim analysis, data is used of the first 507 enrolled participants (i.e. ordered by randomization date) until 6 months follow-up. For the second analysis, data is used of all enrolled participants until 6 months follow-up. The goal of the interim analyses (at both time points) is to estimate the incidence rate ratio of symptomatic Ng plus CT. Estimates will be based on a Poisson regression model (or a negative binomial regression model if there is overdispersion) with number of symptomatic diagnoses as dependent variable, arm and hospital as independent variables and log(number of visits) as offset. This model will provide estimates of the incidence rate in each arm and the incidence rate ratio (no screening versus screening), together with 95% confidence interval. Visits with missing data on the diagnosis of Ng or Ct, will be excluded from the calculation of the incidence rate (excluded both from numerator and denominator).

7. Analysis of main efficacy outcomes: Incidence of Ng plus Ct

In each arm, the incidence of Ng plus Ct will be estimated together with 95% confidence interval. Estimates will be based on a Poisson regression model (or a negative binomial regression model if there is overdispersion) with number of diagnoses as dependent variable, arm and hospital as independent variables, and log(number of visits) as offset. This model will also provide an estimate of the log incidence rate ratio (no screening versus screening), together with 95% confidence interval. The 'no screening' arm is proven to be non-inferior if the upper limit of the 95% confidence interval is lower than $\log(1.25)$.

Visits with missing data on the diagnosis of Ng or Ct, will be excluded from the calculation of the incidence rate (excluded both from numerator and denominator).

In a sensitivity analysis, the numerator of the primary endpoint will only include diagnoses if there was a negative test result at the prior visit.

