8.7 Trial assessments

These assessments will be performed according to standard of care at each participating centre. In certain centres such as HSP the laboratory tests are performed the week before the clinic visit. These laboratory assessments will be considered to be the laboratory results for that particular visit. Participants in the non-screening arm will not be informed of their results at month 3, 6 and 9. They will only be informed about the result of the sample taken at month 0 and month 12.

Screening/enrolment visit (Day 0):

- Eligibility check
- Informed Consent Procedure
- Demographic and question regarding sexual behaviour
- PrEP questionnaire (only at ITM)
- Ask if symptoms compatible with STI
- Physical examination if symptomatic
- STI history last 12 months
- Antibiotic usage last 6 months
- Randomization
- Collection of results of syphilis and HIV testing (performed according to routine practice)
- Sample collection (according to standard practice of the participating sites.):
 - o Urine sample (first-void) (Ng/Ct NAAT)
 - o Pharyngeal swab (Ng/Ct NAAT)
 - o Anorectal swab (Ng/Ct NAAT)

Visit month 3 (can be between one week earlier and 6 weeks later):

- Ask if symptoms compatible with STI
- Physical examination if symptomatic
- STIs diagnosed since last visit (at study site or outside)
- Antibiotic usage
- Question regarding sexual behaviour
- PrEP questionnaire (only at ITM)
- Collection of results of syphilis and HIV testing (performed according to routine practice)

- Sample collection:
 - o Urine sample (first-void) (Ng/Ct NAAT)
 - o Pharyngeal swab (Ng/Ct NAAT)
 - o Anorectal swab (Ng/Ct NAAT)

Visit month 6 (can be between one week early and 6 weeks late):

- Ask if symptoms compatible with STI
- Physical examination if symptomatic
- STIs diagnosed since last visit (at study site or outside)
- Antibiotic usage
- Question regarding sexual behaviour
- PrEP questionnaire (only at ITM)
- Collection of results of syphilis and HIV testing (performed according to routine practice)
- Sample collection:
 - o Urine sample (first-void) (Ng/Ct NAAT)
 - o Pharyngeal swab (Ng/Ct NAAT)
 - o Anorectal swab (Ng/Ct NAAT)

Visit month 9 (can be between one week early and 6 weeks late):

- Ask if symptoms compatible with STI
- Physical examination if symptomatic
- STIs diagnosed since last visit (at study site or outside)
- Antibiotic usage
- Question regarding sexual behaviour
- PrEP questionnaire (only at ITM)

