11.1 Sample size calculation

The primary endpoint is the number of diagnoses of Ng plus Ct over the study period (12 months) whilst individuals are screened vs. not screened.

Numerators: Cumulative number of diagnoses of Ng plus Ct in 12 months in screening/non-screening arms. Each participant can only contribute one diagnosis of Ct and one diagnosis of Ng per (scheduled or unscheduled) visit - regardless of number of sites infected. Thus each participant can contribute up to 2 diagnoses (Ct/Ng) at each (scheduled or unscheduled) visit. The numerator includes laboratory-confirmed diagnoses made between scheduled visits, performed inside or outside of the study.

Denominators: Number of scheduled study visits with available results for the diagnosis of Ng/Ct. The denominator does not include unscheduled visits.

Testing for these infections is performed at each three-monthly visit, i.e. 4 follow-up visits per subject (if complete follow up). Ng/Ct are tested for at 3 sites at each visit – rectum/pharynx and urethra. If a participant is found to be infected with one of these infections at more than one site on a particular visit this is counted as a single infection. If they are found to have both Ng and Ct at a visit this is classified as 2 infections.

Based on the Be-PrEP-ared study from ITM, we assume at baseline visit 79% have 0 diagnoses (pre treatment), 18% have 1 diagnosis (either NG or CT) and 3% has 2 diagnoses (both NG and CT). With screening, the number of diagnoses in the Follow Up (FU) visits depends on number of diagnosis at baseline and is shown below.

	0 diagnoses [#]	1 diagnosis [#]	2 diagnoses [#]	Average nr of diagnoses
0 diagnoses at baseline	86%	13%	1%	0.15
1 diagnosis at baseline	76%	20%	4%	0.28
2 diagnoses at baseline	71%	24%	5%	0.34

[#]These columns refer to the percentage of participants who have 0/1/2 diagnoses at each follow-up visit. In other words, of those with 0 diagnoses at baseline (first row), at each of the visits at 3,6,9 and 12 months, 86% will have 0 diagnoses, 13% will have 1 diagnosis and 1% will have 2 diagnoses.

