Over 4 FU visits, this yields an average of 0.72 diagnoses per subject. Using a Poisson regression model with $\log(\text{number of visits})$ as offset, the 95% confidence interval of the log ratio (no screening vs. screening) is calculated. The 'no screening' arm is considered to be non-inferior if there is an increase of maximal 25% in number of diagnoses (i.e. increase of an average of 0.72 to 0.90 per 4 visits). The 'no screening' arm is proven to be non-inferior if the upper limit of the 95% confidence interval is lower than $\log(1.25)$. The required sample size to detect non-inferiority of the 'no screening' arm is calculated by simulation, assuming no difference between arms.

Assuming that 95% of the participants will have data on all 4 visits, and 5% will have data on only 3 visits, the required sample size to obtain 80% power is 912. Assuming an additional 10% drop out rate we will need to enroll 1014 participants.

The current number of PrEP participants at the ITM/HSP/EH/CHU/UZG is 803/739/290/260/240, respectively. At all 5 centres this number is increasing by approximately 20% per year. 99.7% of these individuals are MSM and over the age of 18. We estimate that 80% of the 2332 PrEP participants in these five centres will agree to participate. This number (n=1866) exceeds the number we need to enroll in the study (n=1014). By the commencement of the study (begin 2020) we estimate we will have 1518/886/464/314/298 individuals in the PrEP cohorts at the ITM/HSP/EH/CHU/UZG whom we will be able to screen for participation.

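### The primary model leaves out baseline Ng/Ct status, a known predictor that the trial already collects: a modest missed efficiency (about 7% of variance), not an error

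*SAP*

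**What the plan says.** SAP 7 analyses the number of Ng plus Ct diagnoses by Poisson regression, or negative binomial regression if there is overdispersion. The terms are those written out for the interim analyses in SAP 6, differing only by a comma: "arm and hospital as independent variables and log(number of visits) as offset". Protocol 11.3.2 has arm and a random intercept for site. Neither contains baseline Ng/Ct status, and neither plans an adjusted sensitivity analysis.

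Protocol 11.1 treats baseline status as a predictor: "With screening, the number of diagnoses in the Follow Up (FU) visits depends on number of diagnosis at baseline". It gives the baseline mix ("we assume at baseline visit 79% have 0 diagnoses (pre treatment), 18% have 1 diagnosis (either NG or CT"), with the remaining 3% having both infections. It then tabulates, for each baseline class, the percentages with 0, 1 and 2 diagnoses at a follow-up visit and the average:

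- "0 diagnoses at baseline 86% 13% 1% 0.15"
- "1 diagnosis at baseline 76% 20% 4% 0.28"
- "2 diagnoses at baseline 71% 24% 5% 0.34"

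The baseline result exists in both arms. Protocol 8.7 lists urine, pharyngeal and anorectal samples at day 0. It says of the non-screening arm: "They will only be informed about the result of the sample taken at month 0 and month 12". Protocol 8.1.2 has positives at that visit treated whatever the allocation. The samples follow each site's standard practice (Protocol 8.7 and the footnote to Table 2).

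**The concern.** The power simulation generates its outcomes from a variable that the analysis then ignores. The rate ratios in the table are 0.28/0.15 = 1.87 and 0.34/0.15 = 2.27. The sample is taken before care differs between the arms, so the variable is a legitimate adjustment covariate. Without it, predictable differences between participants become unexplained variation in the comparison that is set against log(1.25). A trial planned at exactly 80% power has reason to use a predictor that it has already identified and measured.

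**Working it through.** **Inputs (Protocol 11.1).** Baseline mix 0.79/0.18/0.03; the table above; 95% of participants with 4 visits and 5% with 3; margin log(1.25) = 0.2231; true ratio 1; 912 evaluable, so 456 per arm with 1:1 allocation. The table describes follow-up with screening. The same dependence on baseline is taken in both arms, in line with the plan's assumption of no difference.

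**Mean.** 4 × (0.79×0.15 + 0.18×0.28 + 0.03×0.34) = 4 × 0.1791 = 0.7164. The plan agrees: "Over 4 FU visits, this yields an average of 0.72 diagnoses per subject".

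**Variance of the 4-visit count.**
- Per-visit variances are 0.17 − 0.15² = 0.1475, 0.36 − 0.28² = 0.2816 and 0.44 − 0.34² = 0.3244.
- Within baseline classes: 4 × (0.79×0.1475 + 0.18×0.2816 + 0.03×0.3244) = 0.7078.
- Between classes: 16 × (0.035355 − 0.1791²) = 0.0525.
- Total 0.7602. Variance/mean is 1.061 overall and 0.7078/0.7164 = 0.988 within classes. The between-class share is 0.0525/0.7602 = 6.9%.

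**Standard errors at 912.** Mean visits are 3.95, so the expected count is 0.7164 × 3.95/4 = 0.7074.
- Poisson model-based SE: √(2/(456×0.7074)) = 0.0787.
- True SE, unadjusted: 0.0787 × √1.061 = 0.0811.
- True SE, adjusted: 0.0787 × √0.988 = 0.0783, which is 3.5% lower.

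**The plan's figure first.** Power of the unadjusted Poisson interval is Φ((0.2231 − 1.96×0.0787)/0.0811) = 80.2%. The formula reaches 80% at N = 908 against the stated 912, and 912/0.90 rounds up to 1014. The stated figures reproduce.

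**With and without baseline class (hospital not simulated):**

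| Interval | Power by formula | Simulated, 4,000 trials | Mean reported SE | N for 80% |
|---|---|---|---|---|
| Poisson | 80.2% → 81.0% | 80.4% → 80.7% | 0.0788 → 0.0790 | 908 → 890 |
| Robust SE | 78.6% → 81.4% | 78.7% → 81.0% | 0.0810 → 0.0782 | 946 → 882 |

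The simulated variance of the log rate ratio fell by 7.0%. A separate run of 1,500 trials gave 80.3% → 81.1% (Poisson) and 78.2% → 81.5% (robust). A run of 500 trials with negative binomial fits gave SE 0.0812 → 0.0794 and power 81.2% → 83.4%. Its power levels are uncertain by about √(0.8×0.2/500) = 1.8 points, but the direction agrees.

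**Why the Poisson width does not move.** The model-based Poisson SE depends on expected counts, which the covariate leaves almost unchanged. Adjustment narrows the estimator's actual spread, not the reported interval.

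**Extra person-level heterogeneity (an assumption; no figure in the documents).** With gamma variance 0.5 and 1.0, the variance reduction falls to about 5% and 4%, and the power gain is about 0.5 to 2 points.

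**The case against.** The strongest reply is that little is at stake. Only 21% of participants are in the higher-rate classes, so a near-doubling of the rate becomes 6.9% of the variance. Under the model that SAP 7 names first, the reported interval does not narrow and the gain is worth about 908 − 890 = 18 participants. The 2-to-3-point gain needs an interval that reflects dispersion. A robust SE is in neither document. The negative binomial fallback is in the SAP, but without a switching criterion. With variance/mean of 1.06, a 5% one-sided score test for overdispersion fired in only 36% of 2,000 simulated trials, so under such a rule Poisson would usually stay. The table is also slightly underdispersed within classes, so the adjusted robust SE falls below the Poisson SE, a value that neither planned model can return. All of this stands, and it limits the size of the point.

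Protection against chance imbalance adds little as a separate argument. Randomisation is blocked by site only, and imbalance in baseline status moves the log ratio with SD √(0.0811² − 0.0783²) ≈ 0.021. That is the same variance reduction seen from another side. What remains is procedural: SAP 4.2 will note imbalances but states no analytic response, so any later adjustment would be post hoc.

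The covariate is also imperfect. Month-0 sampling follows site practice, and Protocol 1 says that some Belgian PrEP centres test only one anatomical site. The hospital term absorbs only part of any unevenness.

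The reply does not remove the point. On the plan's inputs adjustment does not reduce power under either interval. Because the rate ratio is collapsible under a log link, adjustment also leaves the estimand unchanged.

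**Conclusion.** A modest missed efficiency. On the plan's own table, leaving out baseline status forgoes about 7% of the variance of the log rate ratio. That is worth about 1 power point or less with the default Poisson interval, and about 2 to 3 points (about 78.5% to 81%) with one that reflects overdispersion. These figures rest on the table holding in both arms and on complete baseline data; extra heterogeneity would shrink them.

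A reader might infer three stronger things that the documents do not support:

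- **That the trial is underpowered and adjustment restores it.** The stated 80% at 912 was set for the unadjusted Poisson interval, and it reproduces.
- **That the planned confidence interval is generally too wide, or the comparison biased.** The Poisson width is unaffected, and randomisation protects the unadjusted comparison.
- **That the symptomatic-infection model in SAP 8.2 needs the same term.** The table concerns all diagnoses. No figure links baseline status to later symptomatic infection, and Protocol 7.2 excludes people with symptoms of proctitis or urethritis at entry.

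**What to change.** In SAP 7, add the number of Ng/Ct diagnoses at month 0 as a prespecified categorical independent variable (0, 1, 2, missing) next to arm and hospital. Keep the model without it as a supportive analysis. The missing category keeps participants without a month-0 result in the analysis. Make the change before database lock, the point by which SAP 1 requires the plan to be final. Leave 8.2 as it is.

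The cost is one line of text and a rule for coding baseline results. Month-0 sampling follows local practice, so the report should show by hospital how many participants lack a result and, where known, how many were not sampled at all three sites.

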5 TRIAL DESIGN

This study is a multi-centre, controlled, randomized trial of 3x3 Ng/Ct screening (comparator) vs. no screening (intervention). It will be performed in the PrEP cohorts situated at the ITM, HSP, CHU, UZG and EH. All men in follow up at these five centres who report having had sex with another man in the previous year and are enrolled for PrEP follow up will be eligible to participate in the study. After signing informed consent participants will be randomized via a computer-generated schema to either 3x3 screening or no Ng/Ct screening (see section 8.3). In both arms, participants will be followed up in an identical fashion including 3x3 screening. The only difference between the arms will be that in the screening arm, Ng/Ct results will be sent by the STI Laboratory to the study physicians and these participants will be treated and partner contact tracing will be done. The STI Laboratory will only process the samples/report the results from the non-screening arm at the end of the study. In both arms, all individuals with symptoms compatible with Ng or Ct will be tested and treated for these infections according to current best practice guidelines. At the end of the 12-month study period, participants whose most recent tests were positive for Ng or Ct will receive treatment for these.

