8.4 Blinding

This study will be unblinded.

Study Participants: The participant will not be explicitly informed to which intervention arm they have been randomized. However it will not be possible to completely blind the participants to which arm they are in, since those in the screening arm who test positive will be recalled for treatment of an asymptomatic infection. In addition, participants will be able to see which arm they are in the 3 weeks after enrolment if they login online to obtain their Ng/Ct results (a service that is in the process of becoming available to all PrEP recipients). If they are in the screening arm they will be able to see either a positive or a negative result for Ng/Ct. If they are in the no-screening arm, no test result will be visible. From this they will be able to deduce which arm they are in.

Doctors and study nurses: The attending doctors will not be blinded. Blinding the attending doctors would be very difficult within this study design as a week after each study visit, the doctors will receive the results of the Ng/Ct screening tests, but only for the participants in the 3x3 screening arm. At this point the doctor will be able to deduce which arm the participant is in. As a result, we have decided that the attending doctors will not be blinded to study arm allocation.

Statistician: The study statistician will be blinded until the statistical analysis plan (SAP) is approved.

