8.10 Laboratory procedures

Ng/Ct testing:

Laboratory testing for Ng/Ct from HSP and EH will be performed at the LHUB and for all specimens from the ITM, CHU, UZG at their STI laboratories.

- CT/NG molecular testing will be performed on urine, anorectal and pharyngeal samples.
- Each laboratory will pool each individual's pharyngeal, rectal and urine specimens at each visit and thereby conduct one NAAT (Nucleic Acid Amplification Test), instead of three, according to a validated pooling strategy. Two laboratories participating in this study have published studies validating this pooling strategy [47, 48]. Another pooling strategy validated by ITM will be published soon. Pooling will considerably reduce laboratory costs.
- In case a sample is found to be positive for Ct, the samples will be sent to the Reference STI Laboratory (ITM) where an additional test will be performed to differentiate L versus non-L strains according to current routine care at each centre.

- All study samples found to be positive for Ng or Ct will be stored at each centre until the end of the study and will then be sent to the ITM for long-term storage (future STI research).

HIV and syphilis testing:

- Syphilis, HIV testing will be performed according to each laboratory algorithm as in routine practice

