9.3 Intervention schedule

Participants in the intervention arm will **not** be screened for Ng/Ct for a period of 12 months, in reference to the routine practice of screening (and treating screening-positive) participants every 3 months.

More specifically, participants in the intervention arm will have 3 site (urethra, pharynx and rectum) sampling performed every 3 months but these testing results will only be reported at the end of the 12 month period.

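### SAP 6 counts only visits with an Ng/Ct result in the interim symptomatic rate, without saying whether the withheld no-screening results are available at the looks

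*SAP*

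**What the plan says.** SAP 6 plans looks once 50% and 100% of recruits have passed month 6. The model is Poisson (negative binomial if overdispersed) for symptomatic diagnoses, with arm and hospital as covariates and log(number of visits) as offset. The exclusion rule is "Visits with missing data on the diagnosis of Ng or Ct, will be excluded from the calculation of the incidence rate", and it removes such visits from numerator and denominator alike. The first look uses the first 507 participants to 6 months. For the second, "For the second analysis, data is used of all enrolled participants until 6 months follow-up".

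SAP 5.2 counts in the denominator only scheduled visits with an available result. The numerator also takes laboratory-confirmed diagnoses made between visits. The symptomatic endpoint is built the same way.

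On the no-screening results, Protocol 5 and SAP 2.1 say "The STI Laboratory will only process the samples/report the results from the non-screening arm at the end of the study". Protocol 9.3 says "these testing results will only be reported at the end of the 12 month period", and Protocol 8.7 says "Participants in the non-screening arm will not be informed of their results at month 3, 6 and 9". In both arms, participants with compatible symptoms are tested and treated, and every scheduled visit includes the item "Ask if symptoms compatible with STI".

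**The concern.** The exclusion rule suits a final analysis in which every result exists. At the looks, the month 3 and month 6 results of one arm are withheld by design, and no section gives them to the interim statistician.

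If they are unavailable, the rule works differently in the two arms. A no-screening visit qualifies only if symptoms prompted a test, so qualifying visits are selected on the outcome. The screening arm keeps all its visits. Removing a visit from both numerator and denominator does not protect the ratio, because the visits removed are those without a symptomatic diagnosis. Between-visit diagnoses add to the numerator and nothing to the denominator.

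At stake is the trial's main safety comparison, which is judged against a more than two-fold excess. The error would be a false signal against no screening, or a model that cannot be fitted and has no written substitute.

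**Working it through.** **Plan's own figures.** The documents give no interim ratio, so only the sample can be reproduced. 912/0.9 = 1013.3, rounded up to 1014 (Protocol 11.1). 1014/2 = 507 (SAP 6), or about 253 per arm. With two follow-up visits each, that is 506 visits per arm.

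**Timing.** At 127 recruits a month (Protocol 11.2), 507 are enrolled after 507/127 = 4.0 months. The first look then falls at month 10, or 11.5 with the 6-week visit window. The earliest month 12 visit, one week early, is at about month 11.8, so release at month 12 does not help the first look. The second look falls at month 8 + 6 = 14, up to 15.5. By then (14 − 12)/8 = 25% to (15.5 − 12)/8 = 44% have reached month 12. Under the end-of-study wording, nothing has been released.

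**Inputs if only symptom-prompted results exist.** The only documented anchor is Protocol 10.1.1: over 10% a year for symptomatic urethral Ng. Everything else is assumed, with equal true rates in both arms:
- r, symptomatic Ng plus Ct diagnoses per year: 0.1 to 0.3
- s, share of diagnoses made at scheduled visits: 0.1 to 0.5
- p, positivity of symptom-prompted tests: 0.3 to 0.8

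**Formulas.** Diagnoses per 3-month interval: λ = 0.25r.
- Share of no-screening scheduled visits with a result: q = λs/p.
- Share of no-screening participants with a log(0) offset: (1 − q)².
- Screening rate per visit: λ.
- No-screening rate with zero-visit participants dropped: [2λs + 2λ(1 − s)·q(2 − q)]/(2q), where q(2 − q) is the chance of at least one qualifying visit.
- Ratio: s/q + (1 − s)(2 − q).

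**Mid-range (r = 0.2, s = 0.25, p = 0.5).** q = 0.25 × 0.2 × 0.25/0.5 = 0.025. Log(0) share = 0.975² = 95.1%. Qualifying visits = 506 × 0.025 = 12.65, against 506. Ratio = 0.25/0.025 + 0.75 × 1.975 = 10 + 1.48 = 11.5. A participant-level Poisson fit with arm and hospital gave a median of 11.2.

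**Range over 27 input sets (10,000 runs each, first look).** q runs from 0.3% to 12.5%, the log(0) share from 77% to 99%, and qualifying visits from 1.6 to 63. The median ratio is 4.9 to 36. It is above two in 77% to 100% of computable runs and not computable in 0% to 20%. In the regression fits (six sets), the lower 95% limit was above 1 in 90% to 100% of fitted runs, so the interval gives no protection.

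**Where the ratio equals two.** Solving s/q + (1 − s)(2 − q) = 2 gives q = 24% for s = 0.1 and q = 41% for s = 0.5. The effect fades only if far more visits have results than the grid implies.

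**Other handling and inputs.**
- Baseline visit counted (its result is known in both arms): ratio = 3/(1 + 2q), from 3/1.25 = 2.4 to 3/1.006 = 3.0.
- r = 0.5, p = 0.2, s = 0.75 to 0.9: ratio 2.0 down to 1.7.
- All diagnoses between visits and no scheduled result: no denominator, so not estimable.
- Second look: median 1.1 to 2.4 if results are released at month 12, 4.9 to 35 if only at study end.

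**Attended-visit denominator (95% attendance and 5% failed symptom tests assumed).** The median is 0.99 to 1.01 with no true difference. The first-look ratio exceeds two by chance in 5.3%, 1.3% and 0.2% of runs at 0.1, 0.2 and 0.3 per year. With a true ratio of 2.5 it exceeds two in 75% to 88% of first-look runs.

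**The case against.** The premise is not established. A reader might infer that the no-screening samples will be untested at the looks. The documents do not support that. The sentence in Protocol 5 and SAP 2.1 joins processing and reporting with a slash, and most other sections fit on-time testing with reporting withheld. Protocol 8.4 says "If they are in the no-screening arm, no test result will be visible". Protocol 8.10 has each laboratory pool specimens and run one NAAT per visit, with no distinction by arm, and adds "All study samples found to be positive for Ng or Ct will be stored at each centre until the end of the study". Protocol 10.1.1 and 10.2 provide for recording all STIs in the eCRF and collecting them centrally. If results are on time and reach the statistician, there is no distortion.

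This stands as far as it goes, but it does not close the gap. Protocol 12.2 has data entered at the sites, and Protocol 5 sends timely results to study physicians only in the screening arm. No separate route for withheld results is described.

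A reader might also infer that the trial would be stopped on a false signal. That goes too far. Protocol 10.1.1 and Appendix 1 let the DSMB and the statistician choose threshold and method. Crossing two-fold calls for considering a stop, and Protocol 8.12.4 leaves the decision to the steering committee after consulting the DSMB. An almost empty denominator would probably be noticed. The replacement would then be chosen after seeing data by arm, because SAP 6 has no fallback.

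Finally, the numerical range depends on assumed inputs and on dropping log(0) participants, a step the SAP does not prescribe. That is correct, and the range is illustrative only.

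**Conclusion.** The point holds in conditional form and should be fixed. SAP 6 ties the interim symptomatic rate to availability of a result that one arm withholds, and neither document says it is available at the looks. If it is not, the ratio is either not estimable or, for most plausible inputs, biased upward with no true difference. The direction follows from the plan's own rules; the size does not. About 11 is the mid-range value with zero-visit participants dropped, and 2.4 to 3.0 applies if baseline is counted. Some inputs bring it to two or below, so inflation past the trigger is not certain. The primary analysis is unaffected. Confidence is medium because the laboratory timing is ambiguous.

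Protocol 3 says exceeding a threshold leads to stopping, whereas the committee section, 10.1.1 and Appendix 1 speak of considering it. That is a separate inconsistency and adds no weight here.

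**What to change.** In SAP 6, for the symptomatic endpoint:
- Use as offset in both arms log(attended in-window scheduled follow-up visits at which symptoms were assessed), whether or not the routine Ng/Ct result has been released.
- Exclude a visit only if symptoms called for a test and no valid result was obtained. Participants with no attended follow-up visit do not contribute.
- Keep the SAP 5.2 numerator, the 507-participant and 6-month cuts, and the visit-based scale.
- State whether withheld no-screening results are generated on schedule and available to the interim statistician, and reconcile the end-of-study and end-of-12-months wordings.

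This takes a few sentences and no extra testing, because attendance, symptoms and symptom-prompted results are already collected. The small downside is that the interim denominator differs slightly from the final one in SAP 8.2, which need not change. Separately, the stopping wording in Protocol 3 should be reconciled with the other sections.
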